# 6. **OBJECTIVES**

### 6.1 Primary:

To evaluate the safety and tolerability of multiple doses of DAR-901, at different dose levels, administered to healthy HIV-negative and –positive adults by intradermal injection.

### 6.2 Secondary:

To characterize the immunogenicity of multiple doses of DAR-901 at different dose levels, with emphasis on the cytokine responses to DAR-901 soniciate (i.e., IFN- $\gamma$  secretion and Elispot).

# 7. INVESTIGATIONAL PLAN

### 7.1 Overall Study Design

Overall study design is presented in Section 2.4, including

- Dose Groups (Table 2-1)
- Enrollment Process (Section 2.4.1)
- Study Structure (Section 2.4.2)
- Potential protocol adjustments (Section 2.4.4)
- Risk Management (Section 2.4.2)

#### 7.2 Rationale for Treatment Regimens

### 7.2.1 Dose Levels

The proposed dose levels (0.1, 0.3, 1 mg per dose) are based on

- prior clinical experience with SRL172, a killed whole-cell vaccine prepared from the same genotypic strain grown on agar, and
- mouse immunogenicity studies conducted with DAR-901

*Clinical studies with SRL172.* All clinical studies by Dartmouth investigators were conducted with an adult intradermal dose of 1 mg in a volume of 0.1mL (dose in children < 5 = 0.05 mL). This dose was established in initial studies by British investigators using vaccine prepared by SR Pharma (London). In the DarDar Trial of HIV-infected patients this dose was found to be safe, immunogenic, and effective in the prevention of tuberculosis (see Section 5.5.6). This will be the maximal dose of DAR-901 in the present Phase I study.

#### Mouse immunogenicity studies with DAR-901.

#### 7.2.2 Dose Number and Dosing Interval

The dose number and dosing interval are based on

- prior experience with SRL172, a killed whole-cell vaccine prepared from the same genotypic strain grown on agar, and
- · published experience with other inactivated, whole-cell vaccines

**Dose number.** Inactivated whole cell vaccines are typically administered in a 2- or 3-dose schedule. Studies by Dartmouth investigators with SRL172 have shown safety and immunogenicity with both a 3-dose (Study 005, Table 5-4) and 5-dose schedule (Study 006, Table 5-5). A 3 dose schedule will be employed in the present study and immune assays will also be conducted after 2-doses.

**Dosing interval.** Prior studies by Dartmouth investigators have used 2 month dosing intervals for 3 doses or the first 3 doses (Studies 002-006, Table 5-2). Safety and immunogenicity have been demonstrated with a 3-dose schedule at 0, 2 and 4 mos (Study 005, Table 5-4)

#### 7.3 Rationale for Study Design

The study design – randomized, placebo-controlled, double-blind – is consistent with both the study objectives and current principles for the evaluation of multiple dose courses of investigational treatments. In particular, double-blinding avoids bias by the Investigator and subjects in assessing the subjective aspects of the study, particularly adverse events. The first subject is dosed open-label consistent with risk management for a phase 1 study of an immunogenic vaccine.

The study includes both HIV-negative and –positive adults because the target populations for the vaccine include both populations, but their immune response to the vaccine may be qualitatively and/or quantitatively different.

[name] 5/31/15 10:25 AM

Deleted: Table 2-1

Page 35 of 75

Date: 30 March 2015

[name] 5/31/15 10:25 AM **Deleted:** Table 5-4 [name] 5/31/15 10:25 AM **Deleted:** Table 5-5 [name] 5/31/15 10:25 AM **Deleted:** Table 5-2 [name] 5/31/15 10:25 AM **Deleted:** Table 5-4

# 7.4 Maximum Exposures and Maximum Number of Subjects

The maximum exposures to DAR-901, the investigational agent, will be:

- Dose level: 1 mg per dose (see Table 2-1)
- Number of doses: 3 doses over 4 months (120 days)
- Number of subjects: 36 HIV-negative and 16 HIV-positive subjects in planned cohorts

# 7.5 Definitions Applicable to Managing the Study

Treatment-emergent is defined as onset after active engagement in the trial; that is, after the administration of the first injection of study treatment. It is anticipated that treatment-related events may be observed after each injection of study treatment.

# 7.5.1 Definition of a Dose-Limiting Toxicity (DLT) Event

A DLT systemic clinical event is defined as a treatment-emergent systemic clinical event that meets **all** of the following criteria:

- is assessed by the investigator as related or possibly related to study drug (see Section 12.3.3);
- is of severity (see Section 12.3.4) Grade 2 or higher;
- is of duration >48 hours.

A DLT injection site reaction (ISR) is defined as an event that meets both of the following criteria:

- occurs at the injection site;
  - is of severity Grade 3 or higher.

A DLT *laboratory event* is defined as a confirmed, treatment-emergent laboratory finding that meets **both** of the following criteria:

- is *not* considered consistent with a concurrent clinical event that is assessed as not related or unlikely related to study drug (e.g., an accidental injury, new ART); *and*
- based on pre-specified toxicity criteria (see Section 12.5.5), represents an increase of two Grades or more compared to pre-treatment baseline value.

A subject who experiences a DLT event will not receive further doses of study drug. Unblinding may be performed to determine if a DLT event has occurred in a subject receiving DAR-901.

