# 2.4.2.3 Adverse event monitoring

- At all visits subjects will be asked about adverse events and concomitant medications and a detailed injection site assessment will be performed.
- Between scheduled visits, subjects will be monitored by phone contacts twice weekly through +day 28 post-injection. Subjects will be provided a thermometer to measure body temperature and a ruler to measure injection site reactions. To assure accurate reporting at the scheduled phone calls, subjects will be provided a memory-aid diary to record findings and symptoms daily.
- Digital photographs will be obtained of injection site reactions that include skin breakdown, pustules or abscess
- Subjects whose clinical course suggests secondary complications, e.g., sterile or infected abscesses, will be asked to return to the clinic for evaluation by the investigator.
- Safety laboratory tests will be performed as detailed below. Subjects with treatment-emergent abnormalities meeting predefined toxicity grades will have study treatment discontinued (see Section 7.5.1).
- Subjects will be discontinued from study treatment (see Section 7.6.1) if they experience a doselimiting toxicity (DLT) event, either systemic, local to the injection site, or demonstrated on laboratory tests (see Section 7.5.1 for details).

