# 7.6 Procedures for Managing the Study

# 7.6.1 Discontinuing Study Treatment in Individual Patients

Study treatment may be discontinued in an individual patient for *any* of the following reasons:

- The subject withdraws from study participation by their own decision ("withdrawal of consent"); this may happen at any time and for any reason without prejudice for their continued care.
- The subject has a DLT event as defined in Section 7.5.1.
- The Investigator determines, based on their judgment, that discontinuation of study treatment is in the subject's best interest, e.g., due to an adverse event, noncompliance, or any reason, whether or not related to study drug or study procedures.

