### 12.1.3 Serious Adverse Event (SAE)

- An AE is serious when the subject outcome is one or more of the following:
  - Death.
  - Life-threatening, meaning that the subject was at immediate risk of death from the event at the time that the event occurred. It does not include an event which hypothetically might have caused death if it occurred in a more severe form.
  - Hospitalization, initial or prolonged, meaning that a hospital admission and/or prolongation of a
    hospital stay was required for the treatment of the AE, or occurred as a consequence of the event.
    It does not include a pre-planned elective hospital admission for treatment or diagnostic
    procedures, or, in general, a hospital admission of less than 24 hours duration.
  - Disability or incapacity that is persistent or significant.
  - Congenital anomaly or birth defect.
  - Important medical event that, although not immediately life-threatening, requires intervention in order to prevent one of the other serious outcomes listed above. Examples of such events are allergic bronchospasm requiring intensive treatment in an emergency room or at home; blood dyscrasias or convulsions that do not result in hospitalization; or the development of drug dependency or drug abuse.

<sup>22 A medical product may be a drug or a device being used either prior to or after regulatory approval. The medical product in this protocol will hereafter be referred to as study drug (synonym: investigational agent).

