### 12.3.4 Intensity (Severity)

The intensity (synonym: severity) of clinical AEs (i.e., symptoms reported by the patient and/or signs observed by the investigator) will, in general, be assessed by the Investigator using the five-level grading system (Table 12-2; adapted from CTCAE v4.02 [17]). The system reflects the duration of the event, its impact on the subject's activities, the level of medical intervention required, and, for events assessed as related or possibly related to study drug, the action taken with study drug. The Table below is intended to provide guidance; the investigator should use judgment in assigning an intensity grade to an event. In some instances a single characteristic may determine the grade; in other instances, the overall pattern may be considered more appropriate.

For this purpose, activities of daily living (ADL) are classified into two subsets:

- *Instrumental ADL* e.g., preparing meals, shopping for groceries or clothes, using the telephone, managing money;
- Self-care ADL e.g., bathing, dressing and undressing, feeding self, using the toilet, taking medications, and not being bedridden.

Note that the Sponsor provides specific guidelines for grading injection site reactions (see Section 12.5).

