12.3.4.1 Relationship Between "Intensity" (Severity) and Seriousness in Characterizing Clinical AEs

Intensity (severity) and seriousness are distinct and independent items, with some interrelationship. By definition, clinical events assessed as SAEs meeting criteria for "death" would be Grade 5 and those meeting criteria for "hospitalization" or "life-threatening" would be Grade 4. Typically, events assessed as SAEs based on associated "significant disability" or being "medically important" would be Grade 3 or Grade 4. However, a clinical event may be assessed as Grade 3 and *not* qualify as an SAE; for example, a patient with a history of migraine headaches could have an episode that restricted them to bed for several hours but responded to the usual treatment, ran its usual course and had no sequelae.

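### The over-48-hours condition in the systemic DLT definition has no exemption by grade, so a brief related Grade 4 systemic reaction does not bar further doses

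*Protocol*

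**What the plan says.** Section 7.5.1 defines three kinds of DLT.

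- **Systemic clinical event.** It must meet every one of three criteria: related or possibly related to study drug, Grade 2 or higher, and "is of duration >48 hours".
- **Injection site reaction.** It must occur at the injection site and "is of severity Grade 3 or higher". There is no duration condition.
- **Laboratory event.** This is defined by a rise of two grades or more and is not at issue here.

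The consequence is in the same section: "A subject who experiences a DLT event will not receive further doses of study drug". Section 2.4.2.3 repeats it: "Subjects will be discontinued from study treatment (see Section 7.6.1) if they experience a doselimiting toxicity (DLT) event". Section 7.6.1 lists the reasons for stopping (withdrawal of consent, a DLT, the investigator's judgment) under a permissive lead-in: "Study treatment may be discontinued in an individual patient for". Section 7.7 requires prompt DRC review of any serious adverse event (SAE), and again once two or more subjects in a dose group have a DLT.

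On grading, Section 12.3.4 says of its scale that "In some instances a single characteristic may determine the grade". Section 12.3.4.1 says that SAEs meeting the death criterion "would be Grade 5 and those meeting criteria for 'hospitalization' or 'life-threatening' would be Grade 4". Table 12-2 gives stopping the drug as the typical action for a related Grade 4 event.

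**The concern.** A duration filter is sensible at Grade 2, where it keeps a transient moderate fever or malaise from ending a subject's course. At Grade 4 it works the wrong way. Acute reactions to an injection can be severe and still be over within hours, and the filter takes exactly these out of the stopping rule.

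Two comparisons show the inconsistency. A possibly related Grade 2 event of 49 hours ends dosing, but a related Grade 4 event of 24 hours does not. Within Section 7.5.1 itself, a brief Grade 3 local reaction ends dosing, but a brief Grade 4 systemic one does not.

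What is at stake is the individual subject's protection. Section 5.4 says DAR-901 has not been given to humans before, and each subject is scheduled for three injections. A subject who reacts at Dose #1 has two further injections that no rule bars; one who reacts at Dose #2 has one.

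**Working it through.** The protocol gives no figure to reproduce here; the check is of the rule's logic, followed by a rough frequency.

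**1. The rule over grade and duration.** For a related systemic event, a DLT now requires Grade ≥2 and duration >48 h. The proposed rule is Grade 2 or 3 with duration >48 h, or Grade ≥4 at any duration.

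| Grade | Duration | DLT now | DLT under proposed rule |
|---|---|---|---|
| 1 | ≤48 h | no | no |
| 1 | >48 h | no | no |
| 2 | ≤48 h | no | no |
| 2 | >48 h | yes | yes |
| 3 | ≤48 h | no | no |
| 3 | >48 h | yes | yes |
| 4 | ≤48 h | **no** | **yes** |
| 4 | >48 h | yes | yes |

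Three of the eight cells are DLTs now and four would be after the change: one added, none removed. Extending the any-duration limb to Grade 3 would make it five.

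**2. Can a Grade 4 event be brief on this scale?** Table 12-2 associates Grade 4 with possibly permanent symptoms, but Section 12.3.4 lets one characteristic set the grade. Section 12.3.4.1 assigns Grade 4 to SAEs meeting the life-threatening or hospitalization criteria and attaches no duration to this. A life-threatening allergic reaction that resolves in hours therefore qualifies.

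**3. Does other text supply a mandatory stop?**

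- Table 12-2: labelled typical action, in a table that Section 12.3.4 describes as guidance.
- Section 7.6.1: permissive.
- Section 7.7, SAE review: leads to a recommendation about study conduct.
- Section 7.7, two-DLT notice: does not count these events.

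None of these binds. A brief related Grade 3 event that is not serious triggers neither the SAE route nor the DLT route.

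**4. How often?** Table 5-5 reports that none of the SAEs in the DarDar trial was considered related to immunization, so 0 of 1006 SRL 172 recipients. The exact one-sided 95% upper bound is 1 − 0.05^(1/1006) = 0.00297, or 0.30%. Section 7.4 gives a maximum of 36 + 16 = 52 DAR-901 recipients. DAR-901 is a new product, so 1% and 5% are added as assumptions; the protocol gives no such rates.

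| Rate p | At least one of 52: 1 − (1 − p)^52 | Expected among 52: 52p | At least two of 10, X ~ Bin(10, p) |
|---|---|---|---|
| 0.30% (upper bound) | 14% | 0.15 | 0.04% |
| 1% (assumed) | 41% | 0.52 | 0.4% |
| 5% (assumed) | 93% | 2.6 | 8.6% |

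The last column takes the ten DAR-901 subjects in one of cohorts A1 to A3. Unless the rate is well above the SRL 172 experience, the two-DLT notice would seldom be affected.

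**5. Effect on cohort completion.** Under Section 7.5.2 a subject stopped for a DLT counts as complete; one stopped at discretion before finishing does not. Section 7.5.3 needs 8 complete of 10. One discretionary stop leaves 9 and two leave 8, so no replacement is needed; three leave 7, so one is needed. The effect is small.

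**The case against.** The literal reading is not in dispute; the argument is about weight.

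- **Several safeguards surround such an event.** A life-threatening or hospitalization event is an SAE. Sections 12.4.1 and 12.4.2 require immediate entry, automatic notice to the Medical Monitor, and initial notification within 24 hours that states whether drug was stopped. A single SAE goes to the DRC, a more sensitive trigger than two DLTs.
- **There is time to decide.** Doses are 60 ± 7 days apart, so re-dosing would need a deliberate choice after that review.
- **Grade 4 is already paired with stopping.** Table 12-2 moves from optional at Grades 2 and 3 to discontinued at Grade 4.
- **The permissive wording of 7.6.1 proves little.** The same lead-in covers DLTs and withdrawal of consent, where stopping is certain.
- **The frequency is generous.** The 0.30% is an upper bound for all related SAEs, of which brief Grade 4 systemic events are only a part.
- **Not every acute reaction is Grade 4.** The SAE example in Section 12.1.3, "allergic bronchospasm requiring intensive treatment in an emergency room or at home", is listed among events that are not immediately life-threatening. Section 12.3.4.1 would typically put it at Grade 3 or 4. If graded 3, the Grade 4 change would miss it.

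These points stand as limits on likelihood. They make re-dosing after a brief Grade 4 reaction improbable and the 14% a ceiling if the SRL 172 experience applies. They do not supply a bar. Every safeguard listed ends in judgment or a recommendation, and a stopping rule exists so that this decision does not depend on either. That the guidance in Table 12-2 is stricter at Grade 4 than the binding rule is itself a reason to align them. The DRC charter might add a stop, but it is not at hand and Section 7.5.1 does not refer to it.

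**Conclusion.** The concern holds and should be fixed. As written, a related Grade 4 systemic reaction resolving within 48 hours is not a DLT, triggers no mandatory stop and does not count toward the two-DLT notice.

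The consequence is the missing stop for the individual subject. Dose escalation is little affected, because Section 2.4.1 rests it on DRC review of all available data and not on a DLT count.

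The wording is certain; the frequency is not. The 14% assumes that DAR-901 behaves like SRL 172 and uses an upper bound for a broader class of events. The 1% and 5% rows are assumptions. The case for the change rests on how serious one such event could be and how little the change costs, not on its being likely.

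**What to change.** Reword the systemic limb of Section 7.5.1 along these lines: a systemic DLT is a treatment-emergent systemic clinical event, related or possibly related to study drug, that is either (a) Grade 2 or 3 and lasts more than 48 hours, or (b) Grade 4 or higher, whatever its duration.

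Extending (b) to Grade 3 would match the injection-site limb and also cover acute reactions graded 3. It would stop more subjects, so it is a choice for the sponsor and the DRC.

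Sections 2.4.2.3, 7.5.2, 7.6.1 and 7.7 all refer to a DLT and need no edit. No visits, tests or subjects are added. The cost is that a subject with a brief related Grade 4 event loses any remaining doses, and with them some three-dose immunogenicity data: at most about 0.15 subjects expected among 52 at the 0.30% rate, or 0.5 at an assumed 1%. That subject would then count as complete under Section 7.5.2.

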# 7.5.3 Definition of a Completed Dose Group

- A dose group is complete when *either* of the following criteria are met:
  - At least 80% of the DAR-901 subjects in the dose-group are complete (that is, 8 of 10 or 5 of 6 subjects, as appropriate; to be determined by an unblinded statistician); *or*
  - the dose-group is terminated under the procedures detailed in Section 7.7.

# 7.6 Procedures for Managing the Study

# 7.6.1 Discontinuing Study Treatment in Individual Patients

Study treatment may be discontinued in an individual patient for *any* of the following reasons:

- The subject withdraws from study participation by their own decision ("withdrawal of consent"); this may happen at any time and for any reason without prejudice for their continued care.
- The subject has a DLT event as defined in Section 7.5.1.
- The Investigator determines, based on their judgment, that discontinuation of study treatment is in the subject's best interest, e.g., due to an adverse event, noncompliance, or any reason, whether or not related to study drug or study procedures.

**Confidential and Proprietary** 

[name] 5/31/15 10:25 AM

Deleted: Table 2-1

DAR-901	Page 37 of 75
Protocol DAR-901-MDES, Version 4.1	Date: 30 March 2015

If study treatment is discontinued prematurely, the reasons will be recorded and, if possible, the EOS visit will be performed as specified (see Section 11). If a subject cannot be seen, attempts will be made to contact the subject by telephone.

### 7.6.2 Replacement of Subjects

A subject who does not meet criteria for "complete" (e.g., withdrawal of consent) may be replaced to assure the requirements for completing a cohort are met. A replacement subject will be identified by a distinctive subject number and will receive the same treatment as the subject being replaced.

### 7.7 Dose Review Committee (DRC)

As part of the comprehensive risk management program, the Sponsor will establish a Dose Review Committee (DRC) comprising two independent physicians with clinical trials experience (preferably including early phase and/or vaccine studies) and a representative of the Sponsor who has prior experience with SRL-172. One of the independent members of the DRC may also serve as Medical Monitor for consultation by the Investigator.

The DRC will serve the following functions:

- Perform the reviews specified in Section 2.4.1, including dose escalation, dose selection, and progression to HIV-positive subjects as specified in a Charter. Majority approval by the DRC is required to proceed.
- Be notified of and review promptly any Serious Adverse Events. If the DRC considers that the SAE may be treatment-related, they may request to be unblinded in order to proceed to a recommendation regarding the ongoing conduct of the Study.
- Be notified and review promptly if two (2) or more subjects in a dose group experience a DLT event. The DRC may request to be unblinded if they judge that necessary in order to provide the Sponsor recommendations regarding the ongoing conduct of the Study.
- Recommendations regarding the conduct of the study may include, but are not limited to, increasing safety monitoring procedures or tests; de-escalating to an intermediate dose level; terminating study treatment in one or more ongoing cohorts.

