# 2.4.1 Enrollment Process

As part of the overall risk management plan (see below for additional provisions), enrollment will proceed as follows:

- The study will start with dose group A1 (HIV-negative, IGRA-negative; 0.1 mg per dose).
  - The enrollment procedure comprises the following steps:
  - The first subject will be dosed with vaccine (Day 1) open-label, observed for 1 hr, and examined on Day 3 (~48 hr post-dosing). If there have been no significant safety-related events, enrollment will proceed.
  - For the remaining 15 subjects in the dose group, treatment will be assigned by randomization for A1-A3 and will be open label for A4, B1 and B2
  - A maximum of five subjects may be randomized per calendar day.
- After all subjects in the dose group have completed Study Day 7 follow-up visit, all available data will be reviewed by the Dose Review Committee (DRC; see Section 7.7 for details). Escalation to the next dose level will be contingent on their recommendation.
- If the DRC approves dose-escalation, then enrollment in dose group A2 will commence, using the same process as described for group A1. Similarly, a dose-escalation review will be conducted after all group A2 subjects complete Day 7 follow-up visit; and, if approved, enrollment in dose group A3 will proceed as detailed above.
- After all subjects in dose group A3 have completed the 7d safety evaluation after dose #3 the available safety data including injection site reactions will be conducted by the DRC, supplemented by the PI and, possibly, additional consultants with relevant expertise (e.g., immunology, tuberculosis).
- If the DRC concludes that the A3 dose level of 1 mg is safe then dose group A4 (HIV-negative, IGRA-positive) will be enrolled and administered the 1 mg dose level. If the DRC determines that the 1 mg dose is not safe then they will recommend one of the lower dose levels from A1 or A2 for A4. Subjects may be enrolled as available, up to a maximum of four subjects per calendar day.
- The dose selection review will also assess the vaccine's safety with regard to its administration to HIV-positive subjects. Progression to Part B will be contingent on that review and on the availability of resources.
- Dose group B1 will comprise HIV-positive, IGRA-negative subjects scheduled to receive DAR-901 at the same dose as the A4 cohort. This dose group will be enrolled using the same dose procedure steps detailed above for dose group A4.

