- Dose group B2 will comprise HIV-positive, IGRA-positive subjects scheduled to receive DAR-901 at the same dose as the A4 cohort.. Enrollment in this dose group may commence following a satisfactory Day 3 safety check for the first subject in dose group A4. Dose group B2 will be enrolled using the same procedure steps detailed above for group A4.

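### The DLT trigger in Protocol section 7.7 counts within one dose group, so two, or at most three, non-serious DLTs split across A4, B1 and B2 at their shared dose require no prompt DRC review

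*Protocol*

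**What the plan says.** Section 7.7 gives the DRC two prompt-review triggers. One is any serious adverse event. The other is to "Be notified and review promptly if two (2) or more subjects in a dose group experience a DLT event". The committee's possible recommendations include "terminating study treatment in one or more ongoing cohorts".

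Table 2-1 and section 2.4.1 define A4 (HIV-negative, IGRA-positive), B1 (HIV-positive, IGRA-negative) and B2 (HIV-positive, IGRA-positive) as distinct dose groups. A4 receives 1 mg if the DRC finds that level safe, and otherwise a lower level. B1 and B2 are each "scheduled to receive DAR-901 at the same dose as the A4 cohort". All three are open label and every subject receives DAR-901.

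Under section 7.5.1 a DLT need not be serious. A systemic event qualifies if it is related or possibly related, Grade 2 or higher, and lasts more than 48 hours. An injection site reaction qualifies at Grade 3. The stated consequence is individual: "A subject who experiences a DLT event will not receive further doses of study drug".

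Section 2.4.1 also schedules reviews. One comes "After all subjects in the dose group have completed Study Day 7 follow-up visit", which is after dose 1. Another precedes A4 and comes "After all subjects in dose group A3 have completed the 7d safety evaluation after dose #3". For Part B, "Progression to Part B will be contingent on that review and on the availability of resources".

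**The concern.** In A1 to A3, each dose level is escalated in a single group with 10 DAR-901 recipients, so a count by group is also a count by dose. In A4, B1 and B2 the same threshold of two applies to one dose divided over three small groups, and the two counts separate.

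The groups overlap in the characteristics that set them apart from A1 to A3. A4 and B2 share IGRA-positive status, and B1 and B2 share HIV-positive status. One DLT in each of two groups can therefore be one signal. Table 2-5 has the groups running almost together (dose 2 in weeks 35-36, dose 3 in weeks 43-44), so subjects in the other groups would go on to their next dose. The DRC may act across cohorts, but its DLT trigger does not look across them.

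**Working it through.** **Check of the plan's own figures.** The protocol gives no operating characteristic for the trigger. The group sizes add up: 30 + 4 + 5 + 5 = 44 and 30 + 6 + 8 + 8 = 52 DAR-901 recipients, as in Table 2-1.

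**Largest number of DLTs with no trigger.** With at most one per group over three groups, the maximum is 3, which is 3/14 = 21% at minimum sizes and 3/22 = 14% at maximum sizes. A fourth must trigger.

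**Given exactly two DLTs, placed at random (no rate needed).** The chance that they fall in different groups is:
- Sizes 4/5/5: (4×5 + 4×5 + 5×5) / C(14,2) = 65/91 = 71%.
- Sizes 6/8/8: (6×8 + 6×8 + 8×8) / C(22,2) = 160/231 = 69%.

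**With an assumed rate.** Let p be the chance that a subject has a DLT over three doses, equal across groups and independent between subjects. Rates of 5% and 10% are assumptions.
- Per-group rule: 1 − Π P(X_i ≤ 1).
- Pooled rule: P(X ≥ 2) over all subjects.
- Gap = pooled − per-group = P(two or more in total, no group with two).

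Example, 4/5/5 at p = 0.10:
- P(X ≤ 1) is 0.9⁴ + 4(0.1)(0.9³) = 0.9477 for n = 4, and 0.9⁵ + 5(0.1)(0.9⁴) = 0.9185 for n = 5.
- Per-group: 1 − 0.9477 × 0.9185² = 0.200.
- Pooled: 1 − 0.9¹⁴ − 14(0.1)(0.9¹³) = 1 − 0.2288 − 0.3559 = 0.415.
- Gap: 0.215, of which 0.184 is exactly two DLTs and 0.031 exactly three.

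**Only DLTs before dose 3.** On the Table 2-5 schedule A4 and B1 receive dose 3 in week 43 and B2 in week 44, so a DLT after dose 3 can spare few or no doses. With risk split evenly over the three doses, the rate before dose 3 is q = 1 − (1 − p)^(2/3): 0.0336 for p = 0.05 and 0.0678 for p = 0.10. The same gap formula is then applied with q.

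| Sizes | p | Per-group | Pooled | Gap, three doses | Gap before dose 3 |
|---|---|---|---|---|---|
| 4/5/5 | 5% | 0.058 | 0.153 | 0.095 | 0.051 |
| 4/5/5 | 10% | 0.200 | 0.415 | 0.215 | 0.143 |
| 6/8/8 | 5% | 0.140 | 0.302 | 0.162 | 0.099 |
| 6/8/8 | 10% | 0.414 | 0.661 | 0.246 | 0.212 |

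(Gaps come from unrounded values.)

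If A4 and only one Part B cohort enroll, the three-dose gap at 5% and 10% is 0.035 and 0.096 (sizes 4/5) or 0.065 and 0.136 (sizes 6/8). If neither enrolls it is zero.

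Each gap is an upper bound on what it counts, because it treats every DLT as non-serious and as falling outside the scheduled Day 7 review. Table 2-5 shows that review in week 29 for A4 and B1. For B2 the table is unclear, but section 2.4.1 says "Dose group B2 will be enrolled using the same procedure steps detailed above for group A4", which can be read to include one.

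**The case against.** The strongest case for the plan is that nothing is misstated. Counting within a group is coherent because the groups differ in HIV or IGRA status, and section 7.3 says that responses in HIV-negative and HIV-positive adults may differ. Much is also covered already:
- A subject with a DLT stops dosing.
- Any single SAE reaches the DRC.
- The Medical Monitor shares in judging relatedness (section 12.3.3) and may sit on the DRC.
- One site sees every open-label event.
- The DRC Charter is not shown and could add triggers.

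These points make the gap modest. They do not close it: differing populations are a reason to keep the separate counts, not to omit a combined one, and informal awareness is not a required review.

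The objection that the pooled rule is stricter also stands in part. Two of 14-22 is 14% to 9% of recipients, against 2 of 10 in A1 to A3. That matters less when the result is a review and not a halt.

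Three stronger readings are tempting but unsupported.
- A reader might take a DLT rate from the predecessor vaccine, for example the 1.2% investigator discontinuations in the phase 3 trial or the 2 of 19 HIV-positive withdrawals after dose 3 in Study 005. Table 5-5 calls all the phase 3 reactions mild or moderate, while a local DLT needs Grade 3. The Study 005 withdrawals carry no grade. Neither supplies a DLT rate.
- A reader might take the three-dose gap as the chance of avoidable dosing. It includes DLTs after the last dose, when review can spare little.
- A reader might add A3 to the count if the shared dose is 1 mg. The DRC will already have reviewed A3 through seven days after dose 3.

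**Conclusion.** The point holds as a limited gap in the trigger. Two, or at most three, non-serious DLTs at the dose shared by A4, B1 and B2 require no prompt DRC review when they fall in different groups and outside the scheduled review after dose 1. The figure of about 70% for exactly two DLTs needs no assumed rate, only random placement. The probabilities by rate depend on assumed DLT rates, independence and equal risk across groups; the before-dose-3 figures also assume an even split of risk by dose and the nominal schedule. On that basis the gap in which a review could still spare a dose is about 5% to 14% at minimum sizes and 10% to 21% at maximum sizes, for rates of 5% to 10%. At these rates it is smaller with one Part B cohort, and it is zero with none.

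This does not show that the plan is unsafe or inconsistent. It is a cheap improvement.

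**What to change.** Keep the per-group trigger, which preserves the population-specific signal. Add one sentence to section 7.7 and to the DRC Charter: the DRC is also notified and reviews promptly when two or more DAR-901 recipients in total across A4, B1 and B2 have a DLT. Leave the action to the DRC, and leave A3 out of the count.

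The change uses DLT data already collected and the existing committee. Its price is more reviews when the true rate is low: at 5%, the chance of at least one trigger rises from 6% to 15% at minimum sizes and from 14% to 30% at maximum sizes.
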